3.0 Objectives

Purpose: to determine the feasibility of treating patients with HDMP + rituximab as a means of debulking prior to initiating venetoclax.

Objectives:

Primary:

1. To determine the percentage of patients who have a reduction of lymphadenopathy (from greater than to less than 5 cm in largest diameter) and/or absolute lymphocyte count (from greater than to less than 25k/uL) following 1 or 2 cycles of HDMP + rituximab (only 1 cycle permitted if subject enrolled after protocol v5 approval).

Secondary:

- 1. To determine the rate of laboratory or clinic TLS with this strategy.
- 2. To determine the safety (CTCAE4) of this approach.
- 3. To determine the overall efficacy (iwCLL) of this overall strategy.
- 4. To determine the percentage of patients who have undetectable minimal residual disease in the bone marrow.

Endpoints:

Primary:

1. Percentage of patients that have a decrease in tumor burden from levels of disease that meet "Medium/High-tumor burden" criteria to "Low tumor burden" criteria for disease burden following a maximum of 2 cycles of HDMP + Rituximab (following a maximum of 1 cycle if subject enrolled after protocol v5 approval).

Secondary:

- 1. Percentage of patients that have a decrease in tumor burden from levels of disease that meet "Medium/High-tumor burden" to meet "Low tumor burden" criteria for disease burden following 1 cycle of HDMP + Rituximab.
- 2. Percentage of patients that have a decrease in tumor burden from levels of disease that meet "Medium/High-tumor burden" to meet "Low tumor burden" criteria for disease burden following 2 cycles of HDMP + Rituximab.
- 3. Rate of laboratory TLS (from start of treatment until completion of venetoclax ramp-up)
- 4. Rate of clinical TLS (from start of treatment until completion of venetoclax ramp-up)
- 5. Adverse events by CTCAE4 definitions
- 6. Overall Response rate, Partial Response rate, and Complete response rate per iwCLL criteria after 9 months of venetoclax and at completion of treatment.
- 7. Undetectable minimal residual disease (MRD) rate based on bone marrow biopsy after 9 months of venetoclax, and at completion of treatment.

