6.5 Cycles 7-24: Venetoclax

Cycles 7-24 are 28 days each in duration

Patients are scheduled to be seen in clinic every 3 months

On Day 1 of Cycles 7, 10, 13, 16, 19, and 22, the following are completed:

- History and physical examination including vital signs.
- Current medications will be recorded in the subject's medical record.
- Laboratory examinations: CBC w/differential, comprehensive metabolic panel, phosphorous, uric acid
- Dispensing of Venetoclax 400 mg PO dose (or highest tolerated dose), 90 day supply.

In addition, on Day 1 of Cycle 10

- CT or MRI of thorax, abdomen, and pelvis. Areas that did not have enlarged lymph nodes (greater than 1.5 cm in long-axis diameter on the prior scan) or spleen may be skipped for this radiographic reassessment.
- Marrow biopsy and aspirate if clinical examination is consistent with a complete remission (ie, absolute lymphocyte count less than 4k/uL) and if clinically indicated to determine subsequent therapy (eg: stopping therapy if undetectable minimal residual disease).

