6.6 End of Study Assessment

Within 2 weeks before or after Cycle 24, Day 28, the following are completed:

- History and physical examination including vital signs.
- Current medications will be recorded in the subject's medical record.
- Laboratory examinations: CBC w/differential, comprehensive metabolic panel.
- Collection of correlative sample.
- CT or MRI of thorax, abdomen, and pelvis.
- Marrow biopsy and aspirate if clinical examination is consistent with a complete remission (ie, absolute lymphocyte count less than 4k/uL) and if clinically indicated to determine subsequent therapy (e.g.: stopping therapy if undetectable minimal residual disease).

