6.7 Long-term follow-up

No long-term follow-up visits are scheduled or required per study.

With patient consent, date of progression or next CLL therapy will be recorded based on chart review if data are available, or phone call no more than every 6 months.

6.8 Subject Withdrawal or Treatment Discontinuation:

Patients who meet or develop the following criteria should be discontinued from the study

- Active HBV infection or hepatitis. Patients who are carriers of hepatitis B at the time of discontinuation from study treatment will continue to be followed for clinical and laboratory signs of active HBV infection and for signs of hepatitis.
- Severe or life-threatening anaphylaxis or hypersensitivity reaction to rituximab. Patients that discontinue rituximab for that reason can continue to receive HDMP and venetoclax if clinically indicated.
- Patients who meet the following criteria should discontinue HDMP: Grade 4 psychosis; Active HBV infection or hepatitis as above. HDMP doses can be delayed for acute infection or as clinically indicated.
- Inability of patient to comply with study requirements
- Determination by the investigator that it is no longer safe for the patient to continue therapy

With the exception of following HBV, patients who withdraw from all study therapy do not have required follow-up visits and can enter long-term follow-up (6.7). With patient consent, date of progression or next CLL therapy will be recorded.

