8.2 International Working Group CLL (iwCLL) Clinical Response Assessment

Criteria for response will utilize the 2008 IWCLL Guidelines for response, which includes clinical, hematological, and bone marrow feature:

Complete response: Requires all of the following for a period of at least two months from completion of therapy:

- Absence of significant lymphadenopathy (e.g. >1.5cm in diameter) on physical exam;
- No hepatomegaly or splenomegaly on physical exam;
- Absence of constitutional symptoms;
- Blood counts within the following values: lymphocytes < 4,000/uL, polymorphonuclear leukocytes >1500/ μ L, platelets >100,000/ μ L, hemoglobin >11.0 g/dL (untransfused); absences of clonal lymphocytes;
- Bone marrow aspirate and biopsy must be normocellular for age with <30% of nucleated cells being lymphocytes. Lymphoid nodules must be absent. If the marrow is hypocellular, a repeat determination should be performed in one month.
- The marrow should be analyzed by flow cytometry and/or immunohistochemistry to demonstrate that the marrow is free of clonal B- CLL cells.
- A CT scan or MRI documenting absence of significant lymphadenopathy should be performed if previously abnormal.

• Patients who fulfill the criteria for CR after induction with the exception of a persistent cytopenia that is believed to be treatment related will be considered CR with incomplete bone marrow recovery (CRi). Additionally, patients who fulfill the criteria of CR with exception of having bone marrow lymphoid nodules will be considered a nodular PR.

Partial response: Requires at least 2 of the following criteria from group A, and at least one of the criteria from group B, and for a period of at least 2 months:

Group A:

- ≥50% decrease in peripheral absolute lymphocyte count from pretreatment value, or less than 4,000/uL
- ≥50% reduction in lymphadenopathy by examination or scan, or less than 1.5cm in size.
- ≥50% reduction in splenomegaly (cm below costal margin) by examination or scan
- ≥50% reduction hepatomegaly (total liver span) by examination or scan
- 50% reduction in marrow infiltrate or B-lymphoid nodules

Group B:

- Polymorphonuclear leukocytes ≥1,500/µL or 50% improvement from pre-treatment value:
- Platelets >100,000/µL or 50% improvement from pre-treatment value;
- Hemoglobin >11.0 g/dl (un-transfused) or 50% improvement from pre-treatment value.

Progressive Disease: Characterized by any one of the following events:

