9.0 Statistical Considerations

9.1 General Considerations

This is a pilot/feasibility clinical trial, with the primary feasibility endpoint being debulking of tumor burden to meet criteria for low Tumor Burden upon the completion of cycle 0

.The primary efficacy endpoint is the percentage of patients that have a decrease in tumor burden from levels of disease that meet "Medium/High-tumor burden" criteria to "Low tumor burden" criteria for disease burden following a maximum of 2 cycles of HDMP + Rituximab (called cycle 0 in the protocol schedule of events).

Tumor burden will be assessed prior to initiation of therapy, and after each cycle of HDMP + Rituximab (maximum 2 cycles). See section 8.1 for the definition of these categories of tumor burden.

The secondary endpoints are as follows:

- Percentage of patients that have a decrease in tumor burden from levels of disease that meet "Medium/High-tumor burden" to meet "Low tumor burden" criteria for disease burden following 1 cycle of HDMP + Rituximab.
- Percentage of patients that have a decrease in tumor burden from levels of disease that meet "Medium/High-tumor burden" to meet "Low tumor burden" criteria for disease burden following 2 cycles of HDMP + Rituximab.
- Rate of laboratory TLS (from start of treatment until completion of venetoclax ramp-up).
 See Appendix B for definition and grading of TLS.
- Rate of clinical TLS (from start of treatment until completion of venetoclax ramp-up)

- Adverse events by CTCAE4 definitions and iwCLL definition for hematologic AEs (see section 10.0 for iwCLL definition of hematologic AE).
- Overall Response rate (ORR), Partial Response (PR) rate, and Complete response (CR) rate per iwCLL criteria after 9 months of venetoclax and at completion of treatment. See section 8.2 for iwCLL criteria for definitions of each level of response. ORR includes all patients who have either a PR or CR.
- Undetectable minimal residual disease (MRD) rate based on bone marrow biopsy after 9
 months of venetoclax, and at completion of treatment. Undetectable MRD is defined as
 less than 0.01% CLL cells.

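### Complete response is tied to a two-month period after therapy that the schedule cannot show for completers, and the plan gives no settled rule for patients without a marrow in the undetectable-MRD rate

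*Combined protocol and SAP*

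**What the plan says.** **Complete response.** Section 8.2 states: "Complete response: Requires all of the following for a period of at least two months from completion of therapy". The list that follows covers examination, symptoms, blood counts, marrow and, if previously abnormal, imaging. Partial response in the same section also needs time, but without reference to the end of therapy: "at least one of the criteria from group B, and for a period of at least 2 months".

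Section 9.1, in line with Section 3.0, gives two reporting times: "Complete response (CR) rate per iwCLL criteria after 9 months of venetoclax and at completion of treatment".

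Section 6.6 sets the last visit: "Within 2 weeks before or after Cycle 24, Day 28, the following are completed". Section 6.7 then says: "No long-term follow-up visits are scheduled or required per study". What remains, with consent, is that the "date of progression or next CLL therapy will be recorded based on chart review if data are available, or phone call".

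**Undetectable MRD.** Section 3.0 lists as a secondary endpoint: "Undetectable minimal residual disease (MRD) rate based on bone marrow biopsy after 9 months of venetoclax, and at completion of treatment". At C10D1, Section 6.5 provides for "Marrow biopsy and aspirate if clinical examination is consistent with a complete remission (ie, absolute lymphocyte count less than 4k/uL) and if clinically indicated", and Section 6.6 repeats the same two conditions at the end of study. Section 4.2, Section 4.0 of the synopsis and Section 8.3 state no condition. The brief procedure list in Section 6.0 of the synopsis states none either.

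**Missing assessments.** Section 9.7.1 counts a subject who cannot be assessed as unfavourable, for the primary efficacy endpoint. Section 9.3 defines a Treated population but does not attach it to the MRD rate. Section 9.9 rules out imputation.

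**The concern.** The CR definition and the times at which CR is reported do not fit together. At 9 months the patient is still taking venetoclax. At completion, the last visit falls too early for two months off therapy to have passed. An analyst must drop the clause, score nobody as CR, or treat everyone as not assessable, and the plan does not choose.

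The MRD problem is one of denominator. Whether a marrow exists depends partly on how well the patient responded and partly on clinical need. A rate among sampled patients is therefore a rate in a selected group, and a rate over all treated patients needs a rule for those without a sample. If that choice is left until results are known, it can depend on them. Since 8.2 also requires marrow for CR, the same gap affects CR.

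**Working it through.** **1. The plan's own sized figure.** The only sized calculation is the Simon design for debulking (stop if 2 or fewer of 10 respond; reject if 9 or more of 17; 30% against 60%). Exact binomial calculation gives type I error 0.0402, power 0.8008 and early stopping 0.3828 under the null, matching the stated 0.04, 80% and 38.3%. It uses neither CR nor MRD.

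**2. Day count.** Inputs: Cycle 1 lasts 35 days (6.3) and later cycles 28 days (6.4). With C1D1 as day 1, the end of cycle k is 35 + 28(k − 1).

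- C10D1 = 35 + 28 × 8 + 1 = day 260, on venetoclax.
- C24D28 = 35 + 28 × 23 = day 679; the window is days 665 to 693.
- Two months is about 61 days: 679 + 61 = day 740.
- Latest scheduled observation after C24D28: 693 − 679 = 14 days, against about 61.

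The synopsis runs single-agent venetoclax to Cycle 26. C26D28 = 35 + 28 × 25 = day 735, so the last visit would fall 70 to 42 days *before* therapy ends. The conflict remains under either reading.

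**3. What the two CR readings give.** Illustration only: assume all 17 complete and the 26.8% CR rate that Section 2.1 of the synopsis cites for venetoclax-rituximab applies. Expected CRs are 17 × 0.268 = 4.6. Scored as failures they become 0/17 (exact 95% CI 0–19.5%). Scored as not assessable, there is no rate.

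**4. MRD denominators.** Assumed counts: 17 treated, 10 sampled, 7 undetectable. Intervals are exact, as in Section 9.7.

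| Rule | Rate | 95% CI |
|---|---|---|
| Sampled patients only | 7/10 = 70.0% | 34.8–93.3% |
| All treated, no marrow = not undetectable | 7/17 = 41.2% | 18.4–67.1% |

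The 17 − 10 = 7 unsampled patients could all be detectable or all undetectable, so the rate for all 17 lies between 7/17 = 41% and 14/17 = 82%. The 41% is the conservative end.

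**5. Can existing visits supply confirmation?** C7, C10, C13, C16, C19 and C22 all include examination and blood count (6.5). Nominal days are 176, 260, 344, 428, 512 and 596. With ±14 days at each visit:

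| Pair | Nominal gap, days | Range |
|---|---|---|
| C7D1–C10D1 | 84 | 56–112 |
| C10D1–C13D1 | 84 | 56–112 |
| C10D1–C16D1 | 168 | 140–196 |
| C22D1–C24D28 | 83 | 55–111 |
| C19D1–C24D28 | 167 | 139–195 |

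Neighbouring visits can fall short of 61 days, so actual dates must be used. If both C7D1 and C13D1 are attended, they are at least 168 − 28 = 140 days apart, so one is at least 70 days from C10D1. That does not hold for a patient who stops early and misses later visits.

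**The case against.** **The reporting times may govern.** One can argue that the specific times in 9.1 override a generic criterion taken over from the 2008 guideline. That is a sensible reading, but it removes a condition that 8.2 states, and no text says it is removed.

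**Some follow-up exists.** Dates of progression or next treatment, where available, give indirect evidence that a response lasted. They do not document examination, counts, marrow or imaging.

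**MRD may already be covered.** Section 8.3 labels marrow assessment the primary analysis of clinical efficacy, which could bring in the failure rule of 9.7.1. But 9.1 defines the primary efficacy endpoint as debulking, and 9.9 points the other way. The label adds to the ambiguity and does not settle it.

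**Unread text.** The marrow rows of the schedule carry a note (e) whose wording was not available in the copy examined. It may say when marrow is taken. This stands, and it lowers confidence in the MRD part.

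**Stronger readings a reader might infer.** One is that the CR rate must be 0%. The documents do not support this: no failure rule extends to CR, and not assessable is equally open. Another is that a sampled-only MRD rate must be too high. The examination condition probably selects favourable cases, but the clinical-need condition has no known direction, so upward bias is likely and not proven.

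**Proportion.** These are secondary endpoints in a 17-patient pilot. That stands and limits the weight of the point.

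**Conclusion.** The point holds within limits.

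- **CR, high confidence.** For patients who complete the planned course, the 8.2 criterion cannot be confirmed at either reporting time: at most 14 scheduled days after C24D28 against about 61. Patients who stop early are outside this statement; some may have later visits off therapy, although 6.8 generally requires none.
- **MRD, moderate confidence.** Available text does not settle how a patient without a marrow counts. On assumed counts, the same data give 70% or 41%.
- **Not affected.** The debulking test and its Simon decision rule. ORR is largely unaffected because PR is not tied to the end of therapy.

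The day counts rest on nominal cycle lengths. The CR and MRD counts are illustrations and not forecasts. Both rules should be fixed before the secondary analysis.

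**What to change.** **(a) CR, Section 8.2.** Define CR at each reporting time as all criteria met at that assessment, with examination and counts also met at another attended visit at least 61 days earlier or later by actual dates, and at any visit between. For patients who stop early, use their own last full assessment and whichever attended visit meets the gap. If none does, report the CR as unconfirmed and leave it out of the main rate. A patient with no marrow is not counted as CR in the main rate; report separately how many meet every other criterion. Label this as on-treatment confirmation that differs from the post-therapy clause.

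**(b) Denominators, Section 9.9.** Report CR and undetectable-MRD rates on the Treated population. Count patients without a marrow as not undetectable and describe this as conservative. Show the number sampled and give the assessed-only rate as a sensitivity analysis, all with exact 95% CIs. State that this is an exception to the no-imputation rule.

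**(c) Reconciliation.** The sponsor must reconcile the marrow passages (Sections 4.0 and 6.0 of the synopsis; protocol Sections 4.2, 6.5, 6.6 and 8.3; note (e) of the schedule) and the passages that end treatment at Cycle 24 or Cycle 26. No clinical rule is proposed here. If the end of therapy moves, the intervals above must be recomputed.

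**Cost.** Amendments to 8.2, 9.9 and the reconciled passages; no extra visits or narrower windows. CR becomes less comparable with reports that use the post-therapy clause, and both rates will be less favourable and may understate the truth.

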8.3 Minimal Residual Disease Assessment

Primary clinical efficacy analysis will be assessment of marrow for detectable CLL after 24 cycles (or sooner if treatment is discontinued early) by flow cytometry and immunohistochemistry per standard practice by local hematopathologist. A threshold of 0.01% will define undetectable versus detectable minimal residual disease (MRD).

8.4 Correlative Studies

Limited correlative studies will be performed in the [name] laboratory to correlate with clinical responses. Samples will be taken at baseline/screening and during treatment and after treatment. However, not all assays will be performed for all time points for all patients, based on sample availability and leukemic cell number. Specimens will be banked in the CLL research consortium tissue repository (see below).

Isolation of leukemic cells by Ficoll-hypaque separation and assessment, which may include:

- ZAP-70 and Immunoglobulin heavy chain variable region (IgVH) mutation in CLL cells
- Genomic assessment including Next generation sequencing or gene expression analysis

Sampling Schedule:

Blood sample for correlative studies will be collected at the following time points:

- Day 1, cycle 0, pre-dose
- Day 1, cycles 1, pre-dose
- End of treatment visit

Sample Collection and Handling Instructions

Blood samples (approximately 40 ml on screening, 10 ml on other time points) will be collected in anti-coagulated (CPT) tubes for pharmacokinetic evaluation. The exact time that the sample is drawn along with the exact time that treatments are administered should be recorded.

Sample Processing

Samples will be processed in the translational lab of [name], with separation of plasma (for blood and apheresis products), followed by isolation of mononuclear cells by Ficoll differential centrifugation, respectively.

Sample Labeling

Each tube must be labeled with the patient's study number and the date and time the sample was drawn. Data should be recorded on the Correlative Study Form, which must accompany the sample(s).

8.5 Specimen Banking

Patient samples collected for this study will be retained at the UCSD School of Medicine ([name] Laboratory). Specimens will be stored indefinitely or until they are used up. If future use is denied or withdrawn by the patient, best efforts will be made to stop any additional studies and to destroy the specimens. Samples will be labeled with the subject's de-identified study number and collection date. The link between study number and medical record number will be viewed over a password secured encrypted server-client.

The following information obtained from the subject's medical record may be provided to research collaborators when specimens are made available:

- Diagnosis
- Collection time in relation to study treatment
- Clinical outcome if available
- Demographic data

9.0 Statistical Considerations

9.1 General Considerations

This is a pilot/feasibility clinical trial, with the primary feasibility endpoint being debulking of tumor burden to meet criteria for low Tumor Burden upon the completion of cycle 0

.The primary efficacy endpoint is the percentage of patients that have a decrease in tumor burden from levels of disease that meet "Medium/High-tumor burden" criteria to "Low tumor burden" criteria for disease burden following a maximum of 2 cycles of HDMP + Rituximab (called cycle 0 in the protocol schedule of events).

Tumor burden will be assessed prior to initiation of therapy, and after each cycle of HDMP + Rituximab (maximum 2 cycles). See section 8.1 for the definition of these categories of tumor burden.

The secondary endpoints are as follows:

- Percentage of patients that have a decrease in tumor burden from levels of disease that meet "Medium/High-tumor burden" to meet "Low tumor burden" criteria for disease burden following 1 cycle of HDMP + Rituximab.
- Percentage of patients that have a decrease in tumor burden from levels of disease that meet "Medium/High-tumor burden" to meet "Low tumor burden" criteria for disease burden following 2 cycles of HDMP + Rituximab.
- Rate of laboratory TLS (from start of treatment until completion of venetoclax ramp-up).
 See Appendix B for definition and grading of TLS.
- Rate of clinical TLS (from start of treatment until completion of venetoclax ramp-up)

- Adverse events by CTCAE4 definitions and iwCLL definition for hematologic AEs (see section 10.0 for iwCLL definition of hematologic AE).
- Overall Response rate (ORR), Partial Response (PR) rate, and Complete response (CR) rate per iwCLL criteria after 9 months of venetoclax and at completion of treatment. See section 8.2 for iwCLL criteria for definitions of each level of response. ORR includes all patients who have either a PR or CR.
- Undetectable minimal residual disease (MRD) rate based on bone marrow biopsy after 9
 months of venetoclax, and at completion of treatment. Undetectable MRD is defined as
 less than 0.01% CLL cells.

